### **7.6.3 Adverse Events Leading to Discontinuation of Study Therapy**

AEs leading to discontinuation will be summarized by treatment group:

- Overall summary of AEs leading to discontinuation by worst CTC grade (any grade, grade 3-4, grade 5) presented by SOC/PT.
- Overall summary of drug-related AEs leading to discontinuation by worst CTC grade (any grade, grade 3-4, grade 5) presented by SOC/PT.

The analyses will be conducted using the 30-day safety window.

A by-subject AEs leading to discontinuation listing will be provided.

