Subjects must be followed for at least 100 days after the last dose of study therapy. Follow-up visit #1 (FU1) occurs approximately 35 days (+/- 7 days) after last dose or coinciding with the date of discontinuation (+/- 7 days) if the date of discontinuation is greater than 35 days after the last dose. Follow up visit #2 (FU2) occurs approximately 80 days (+/- 7 days) after FU1. Survival visits are every 3 months from FU2 until the end of the study (5 years from the primary analysis of DFS) and may be conducted during a clinic visit or via the phone. The co-primary endpoint of this study is DFS in all randomized and in PD-L1 expressers ($\geq 1\%$ membranous tumor staining) and a key secondary endpoint is OS so tracking and reporting the subject's status in the follow up setting according to the protocol guidelines for disease recurrence and survival are critical to the final study analysis. The importance of follow up should be clearly communicated to study subjects.

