4.5.2 Dose Delay Criteria

Dose delay criteria apply for all drug-related adverse events. Treatment delays up to 6 weeks (42 days) from the last dose are allowable.

Nivolumab (or placebo) administration should be delayed for the following:

- Any Grade ≥ 2 non-skin, drug-related adverse event, with the following exceptions:
 - Grade 2 drug-related fatigue or laboratory abnormalities do not require a treatment delay
- Any Grade 3 skin, drug-related adverse event
- Any Grade 3 drug-related laboratory abnormality, with the following exceptions for asymptomatic amylase or lipase, AST, ALT, or total bilirubin:
 - Grade 3 lymphopenia does not require dose delay
 - Grade 3 amylase or lipase abnormalities that are not associated with symptoms or clinical manifestations of pancreatitis do not require a dose delay. It is recommended to consult with the BMS Medical Monitor for Grade 3 amylase or lipase abnormalities.
 - If a subject has a baseline AST, ALT, or total bilirubin that is within normal limits, delay dosing for drug-related Grade ≥ 2 toxicity
 - If a subject has baseline AST, ALT, or total bilirubin within the Grade 1 toxicity range, delay dosing for drug-related Grade ≥ 3 toxicity
- Any adverse event, laboratory abnormality, or intercurrent illness which, in the judgment of the investigator, warrants delaying the dose of study medication.

Subjects who require delay of nivolumab (or placebo) should be re-evaluated weekly or more frequently if clinically indicated and resume nivolumab (or placebo) dosing when re-treatment criteria are met.

Note: per BMS standards, the term “interruption” is reserved for interruption of the actual IV infusion during administration. The terms delay and interruption should not be used synonymously when completing the CRF forms.

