 - Dosing delays to allow for prolonged steroid tapers to manage drug-related adverse events are allowed. Prior to re-initiating treatment in a subject with a dosing interruption lasting > 6 weeks from the last dose, the BMS Medical Monitor must be consulted. Tumor imaging assessments should continue as per protocol even if dosing is interrupted.
 - Dosing delays > 6 weeks from the last dose that occur for non-drug-related reasons may be allowed if approved by the BMS Medical Monitor. Tumor imaging assessments should continue as per protocol even if dosing is interrupted.
- Any adverse event, laboratory abnormality, or intercurrent illness which, in the judgment of the Investigator, presents a substantial clinical risk to the subject with continued nivolumab (or placebo) dosing.

Tumor assessments for all subjects should continue until non-urothelial tract recurrence as per protocol even if study drug dosing is discontinued. Tumor assessments, QoL questionnaires collection and biomarker sampling should continue as per protocol even if dosing is omitted.

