## 6 STUDY PERIODS, TREATMENT REGIMENS AND POPULATIONS FOR ANALYSES

### 6.1 Study Periods

- Baseline period:
  - Baseline evaluations or events will be defined as evaluations or events that occur before the date and time of the first dose of study treatment. Evaluations (laboratory tests and vital signs) on the same date and time of the first dose of study treatment will be considered as baseline evaluations. Adverse Events (AEs) on the same date and time of the first dose of study treatment will not be considered as pre-treatment events.
  - In cases where the time (onset time of event or evaluation time and dosing time) is missing or not collected, the following definitions will apply:
    - ◆ Pre-treatment AEs will be defined as AEs with an onset date prior to but not including the day of the first dose of study treatment;
    - ◆ Baseline evaluations (laboratory tests and vital signs) will be defined as evaluations with a date on or prior to the day of first dose of study treatment.
  - If there are multiple valid assessments on or prior to the first dose of study treatment:
    - [REDACTED]
    - [REDACTED]
    - ◆ For PD-L1, among the biopsy samples records taken prior to or on first dose date (and time if collected), identify first those with quantifiable test result. If there are no records with quantifiable test result, then select those with indeterminant result (“INDETERMINATE”). If there are no records with indeterminant test result, then select those with unavailable result (“NOT EVALUABLE”). If there are no records with unavailable test result, then select those with not reported or not available result (all other records). The latest record will be used as the baseline in the analyses. If there is more than one record for the latest date, then choose the one with the greatest specimen ID.
    - [REDACTED]

- Post baseline period:
  - On-treatment AEs will be defined as AEs with an onset date and time on or after the date and time of the first dose of study treatment (or with an onset date on or after the day of first dose of study treatment if time is not collected or is missing). For subjects who are off study treatment, AEs will be included if event occurred within a safety window of 30 days (or 100 days depending on the analysis) after the last dose of study treatment. No “subtracting rule” will be applied when an AE occurs both pre-treatment and post-treatment with the same preferred term and grade.

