## 6.3 Populations for Analyses

- Enrolled subjects: All subjects who signed the informed consent form and obtained a subject number.
- Randomized subjects: All subjects who were randomized through the IRT.
- Randomized subjects with PD-L1 expression  $\geq 1\%$ : All subjects who were randomized through the IRT with baseline PD-L1 expression  $\geq 1\%$  as stratification factor (source IVRS).
- Treated subjects: All randomized subjects who received at least one dose of any study treatment (nivolumab or placebo).
- Treated subjects with PD-L1 expression  $\geq 1\%$ : All randomized subjects with baseline PD-L1 expression  $\geq 1\%$  as stratification factor (source IVRS) who received at least one dose of any study treatment (nivolumab or placebo).

█ [REDACTED]

█ [REDACTED]

Adverse events leading to dose reduction are AEs with action taken regarding study drug(s) = “Dose was reduced”.

Adverse events will be coded using the Medical Dictionary for Regulatory Activities (MedDRA), and the most recent version of the dictionary at the time of the database lock will be used. Adverse events results will be graded for severity using NCI Common Terminology Criteria for Adverse Events (CTCAE) and the most recent version of the criteria at the time of the database lock will be used.

In the AE summary tables, unless otherwise specified, subjects will be counted only once at the Preferred Term (PT), only once at the System Organ Class (SOC), and only once at subject level for the counting of total number of subjects with an AE. The AE tables will be sorted by the SOCs and then PTs. SOC will be ordered by descending frequency overall and then alphabetically. PTs will be ordered within SOC by descending frequency overall and then alphabetically. The sorting will be done based on the ‘Any Grade’ column of the experimental arm when arms are presented side-by-side.

Unless otherwise specified, the AE summary tables will be restricted to on-treatment events regardless of the causality.

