### **7.6.1 Deaths**

Deaths will be summarized by treatment group:

- All deaths, reasons for death.
- Deaths within 30 days of last dose received, reasons for death.
- Deaths within 100 days of last dose received, reasons for death.

A by-subject listing of deaths will be provided for the all enrolled subjects population.

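### The two summary tables of AEs leading to discontinuation (SAP 7.6.3) use the 30-day window only, so a new AE that starts more than 30 days after the last dose, during a permitted hold, and ends treatment is not counted in them

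*SAP*

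**What the plan says.** SAP 7.6.3 plans two tables by treatment group: AEs leading to discontinuation, and drug-related AEs leading to discontinuation, each by worst grade and by system organ class and preferred term. The window is set in one sentence: "The analyses will be conducted using the 30-day safety window". No 100-day version is named. The section also provides a by-subject listing, with no window stated for it.

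SAP 6.1 defines the window: "AEs will be included if event occurred within a safety window of 30 days (or 100 days depending on the analysis". It applies to subjects who have stopped treatment. The count starts at the last dose, not at the decision to stop. The SAP's general AE conventions restrict AE summary tables to on-treatment events unless otherwise specified.

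The protocol lets a subject stay on study therapy without dosing for longer than 30 days:

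- Section 4.5.2: "Treatment delays up to 6 weeks (42 days) from the last dose are allowable".
- Section 4.5.5, exceptions beyond 6 weeks: "Dosing delays to allow for prolonged steroid tapers to manage drug-related adverse events are allowed", and delays "that occur for non-drug-related reasons may be allowed if approved by the BMS Medical Monitor".
- Section 3.5 gives a rule for the first follow-up visit "if the date of discontinuation is greater than 35 days after the last dose".

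Elsewhere the plan does look beyond 30 days. SAP 7.6.1 tabulates deaths at 30 days and also "Deaths within 100 days of last dose received, reasons for death". Protocol 6.2.2 counts immune-mediated AEs to 100 days after the last dose.

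**The concern.** These tables exist to count the events that ended treatment. The protocol lets treatment end later than the window reaches, so the rule can leave out events of exactly the kind being counted. A subject on hold may develop a new event that forces discontinuation. Examples under Protocol 4.5.5 are grade 3 drug-related pneumonitis or colitis of any duration, or any AE that the investigator judges a substantial clinical risk with further dosing. If that event starts after day 30, its onset falls outside the window.

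In these two tables the rule can only lower the counts. At stake is the completeness of a tolerability summary in patients who were disease-free at entry, for whom the rate of treatment-ending toxicity is part of the benefit-risk judgement. No efficacy test and no error rate is involved.

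**Working it through.** The plan gives no figure to reproduce here. The check is day arithmetic, with every day counted from the last dose.

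**Inputs**

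- Window for both tables: 30 days (SAP 7.6.3, anchored by SAP 6.1).
- Alternative window already defined: 100 days (SAP 6.1).
- Ordinary hold limit: 42 days (Protocol 4.5.2).
- Longer holds: allowed for steroid tapers or approved non-drug-related reasons, with no upper limit stated (Protocol 4.5.5).
- Planned sizes: 700 randomized 1:1, of whom about 294 have PD-L1 ≥1% (SAP 5).

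**Step 1. Uncovered span.** Hold limit minus window: 42 − 30 = 12 days, namely days 31 to 42. In a longer hold the span runs from day 31 to the end of the hold.

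**Step 2. Worked case.** A new AE starts on day 36 of a hold and ends treatment. Since 36 > 30, neither table counts it. Since 36 ≤ 100, a 100-day table would.

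**Step 3. Which events are affected.** Inclusion depends on onset. The AE that caused the hold normally started before it and stays in, even if the decision to stop comes after day 30. Only new AEs with onset after day 30 drop out.

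**Step 4. Effect of a 100-day repeat.** For an ordinary hold the gap falls from 12 days to 0, with a margin of 100 − 42 = 58 days. For longer holds, onsets on days 31 to 100 are counted. Onsets after day 100 are still missed.

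**Step 5. Weight of one missed subject**, assuming every randomized subject is treated:

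- All subjects: 700/2 = 350 per arm; 1/350 = 0.29 percentage points.
- PD-L1 ≥1%: 294/2 = 147 per arm; 1/147 = 0.68 percentage points.

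These are the effects of one hypothetical subject. The documents give no rate of long holds or of new AEs within them, so the number of such subjects cannot be computed. The 12 days are a time span and not a share of events.

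**Step 6. Whether the data exist.** Nonserious AEs are collected for at least 100 days after the last dose (Protocol 6.2.1), and SAEs within 100 days of stopping dosing (Protocol 6.1.1). A 100-day table needs no new collection.

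**The case against.** The best defence is that 30 days is the SAP's working convention, chosen per analysis as SAP 6.1 allows. It is also used for SAEs (7.6.2), dose modification (7.6.4) and AE subgroups (7.6.16). Any fixed window omits later onsets. Deaths are a weak comparator because they often follow the end of treatment, whereas AEs that stop treatment usually begin during dosing. This stands to the extent that the choice is a convention and not an error. The remaining difference is that this table counts treatment-ending events, and the protocol lets treatment end after the window closes.

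The scenario is also narrow. It needs a gap of more than 30 days, a new AE within it, and that AE, not the one behind the hold, recorded as the reason for stopping. An ordinary delay beyond 6 weeks already requires discontinuation. The 35-day rule in Protocol 3.5 only schedules a visit and covers stopping for any reason; it shows that late discontinuation is foreseen, not that new AEs cause it. All of this stands and supports a very small expected effect.

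A reader might infer that the organ class, grade and causality of these events are lost to the report. The documents do not support that. The listing in 7.6.3 has no stated window, and its layout sits in a Data Presentation Plan that is not available. SAP 7.3.1 gives discontinuation reasons by arm, and SAP 7.4.1 lists dosing with the reason for stopping. Serious events have their own listing (7.6.2), and late immune-mediated events may appear in those analyses. SAP 7.6.5 to 7.6.14 and the definition of an AE leading to discontinuation are not visible, so a 100-day summary may already exist there. None of this puts the event into the two 7.6.3 counts.

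Finally, SAP 6.1 does not say whether off-treatment status is judged at onset or at analysis. If at onset, a subject on hold might still be on treatment and the AE might count. Status at analysis is the likelier reading, because the window is measured from the last dose of a subject who has stopped.

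**Conclusion.** The gap is real but small. As written, a new AE that starts more than 30 days after the last dose and ends treatment during a permitted hold does not enter either 7.6.3 summary table. It may still be visible in the listing, in the disposition reasons, or in text that cannot be seen.

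The number affected is unknown and probably very small. Each such subject would lower a table rate by 0.29 points (all subjects) or 0.68 points (PD-L1 ≥1%) at planned arm sizes, if all randomized subjects are treated. The conclusion rests on reading off-treatment status at the time of analysis.

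A reader might infer that the rule favours nivolumab by hiding its toxicity. The documents do not show this: the same window applies to both arms, and nothing gives the frequency of late-onset events in either. No efficacy decision changes. This is a cheap improvement and not a flaw that threatens the safety conclusions.

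**What to change.** Keep the 30-day tables. In SAP 7.6.3, extend the sentence "The analyses will be conducted using the 30-day safety window" with the words *and repeated using the 100-day safety window (Section 6.1)*. Select events by the SAP's own action-taken definition for discontinuation. A short footnote to the 100-day tables should say that counts may differ from the subject-status reasons in 7.3.1 and from the 30-day AE and SAE tables.

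The cost is one sentence, one footnote and four outputs: 2 tables × 2 populations (all treated, and treated with PD-L1 ≥1%). The 100-day tables may show slightly higher rates, and a few events in them will be absent from the 30-day tables. Onsets after day 100 of a very long hold would still be missed.

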### **7.6.4 Adverse Events Leading to Dose Modification**

AEs leading to dose delay/reduction will be summarized by treatment group:

- Overall summary of AEs leading to dose delay/reduction by worst CTC grade (any grade, grade 3-4, grade 5) presented by SOC/PT.
- Overall summary of related AEs leading to dose delay/reduction by worst CTC grade (any grade, grade 3-4, grade 5) presented by SOC/PT.

The analysis will be conducted using the 30-day safety window.

[REDACTED]

**7.6.15 Pregnancy**

A by-subject listing of pregnancy tests results will be provided for randomized female subjects.

**7.6.16 Adverse Events by Subgroup**

Overall summary of any AEs and drug-related AEs by worst CTC grade (any grade, grade 3-4, grade 5) presented by SOC/PT and for each treatment group for the following subgroups:

- Sex (Male vs. Female)
- Race
- Age (< 65 vs. 65 - < 75 vs. 75 - < 85 vs. ≥ 85 vs. ≥ 75 vs. ≥ 65)
- Region (US, EU, ROW)

These analyses will be conducted using the 30-day safety window only.

[REDACTED]

[REDACTED]

[REDACTED]

[REDACTED]

[REDACTED]

[REDACTED]

**7.8.1 Distribution of PD-L1 Expression**

Descriptive statistics of PD-L1 expression will be performed in all randomized subjects, unless otherwise specified:

- Listing of all PD-L1 IHC data.
- Summary of tumor specimen acquisition and characteristics.
- Summary statistics of PD-L1 expression in all randomized subjects with quantifiable PD-L1 expression.
- Cumulative distribution plot of baseline PD-L1 expression versus population percentile in all randomized subjects with quantifiable PD-L1 expression.
- Waterfall plot of Individual PD-L1 expression in all randomized subjects with quantifiable PD-L1 expression.

## 8 CONVENTIONS

The following conventions may be used for imputing partial dates for analyses requiring dates:

- For missing and partial adverse event onset dates, imputation will be performed using the Adverse Event Domain Requirements Specification
- For missing and partial adverse event resolution dates, imputation will be performed as follows (these conventions may change):
  - If only the day of the month is missing, the last day of the month will be used to replace the missing day. If the imputed date is after the death date or the last known alive date, then the latest known alive date or death date is considered as the resolution date.
  - If the day and month are missing or a date is completely missing, it will be considered as missing.
- Missing and partial non-study medication domain dates will be imputed using the derivation algorithm described in Section 4.1.3 of BMS Non-Study Medication Domain Requirements Specification.
- Missing and partial radiotherapy and surgery dates will be imputed using algorithm described in [APPENDIX 2](#).
- For death dates, the following conventions will be used for imputing partial dates:
  - If only the day of the month is missing, the 1st of the month will be used to replace the missing day. The imputed date will be compared to the last known alive date and the maximum will be considered as the death date.
  - If the month or the year is missing, the death date will be imputed as the last known alive date.
  - If the date is completely missing but the reason for death is present, the death date will be imputed as the last known date alive.
- For date of recurrence after start of study therapy, the following conventions will be used for imputing partial dates:
  - If only the day of the month is missing, the 1st of the month will be used to replace the missing day. In case of the date of death is present and complete, the imputed recurrence date will be compared to the date of death. The minimum of the imputed recurrence date and date of death will be considered as the date of recurrence.
  - If the day and month are missing or a date is completely missing, it will be considered as missing.
- For date of recurrence to prior therapies, the following conventions will be used for imputing partial dates:
  - If only the day of the month is missing, the 1st of the month will be used to replace the missing day.
  - If the day and month are missing or a date is completely missing, it will be considered as missing.
- For other partial/missing dates, the following conventions were used:

- If only the day of the month is missing, the 15th of the month will be used to replace the missing day.
- If both the day and the month are missing, “July 1” will be used to replace the missing information.
- If a date is completely missing, it will be considered as missing.

The following conversion factors will be used to convert days to months or years:

$$1 \text{ month} = 30.4375 \text{ days and } 1 \text{ year} = 365.25 \text{ days.}$$

Duration (e.g. time-to onset, time-to resolution) will be calculated as follows:

$$\text{Duration} = (\text{Last date} - \text{first date} + 1)$$

Last known alive date will be defined based on all appropriate dates collected on the CRF.

All statistical analyses will be carried out using SAS (Statistical Analysis System software, SAS Institute, North Carolina, USA) unless otherwise noted.

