3.6.2 Lost to Follow-Up

All reasonable efforts must be made to locate subjects to determine and report their ongoing status. This includes follow-up with persons authorized by the subject as noted above. Lost to follow-up is defined by the inability to reach the subject after a minimum of three documented phone calls, faxes, or emails as well as lack of response by subject to one registered mail letter.

All attempts should be documented in the subject's medical records. If it is determined that the subject has died, the site will use permissible local methods to obtain the date and cause of death.

If investigator's use of third-party representative to assist in the follow-up portion of the study has been included in the subject's informed consent, then the investigator may use a Sponsor-retained third-party representative to assist site staff with obtaining subject's contact information or other public vital status data necessary to complete the follow-up portion of the study. The site staff and representative will consult publicly available sources, such as public health registries and databases, in order to obtain updated contact information. If after all attempts, the subject remains lost to follow-up, then the last known alive date as determined by the investigator should be reported and documented in the subject's medical records.

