#### 4.1.2 Overall Survival

Overall survival (OS) is key secondary endpoint and defined as the time from randomization to the date of death from any cause. For subjects that are alive, their survival time will be censored at the date of last contact date (or “last known alive date”). OS will be censored at the date of randomization for subjects who were randomized but had no follow-up.

Survival follow-up will be conducted every 3 months after subject’s off-treatment date.

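### SAP section 8 dates a death with unknown month to the last known alive date even when the year is known, so it can place the death in a year the record excludes

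*SAP*

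**What the plan says.** The rules for partial death dates are in SAP section 8 (Conventions).

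- **Day missing.** The 1st of the month is used, and then: "The imputed date will be compared to the last known alive date and the maximum will be considered as the death date". The known month and year are kept.
- **Month or year missing.** "If the month or the year is missing, the death date will be imputed as the last known alive date". No comparison with the start of a known year follows.
- **Last known alive date.** "Last known alive date will be defined based on all appropriate dates collected on the CRF". Nothing ties it to the year of death.
- **Other partial dates.** For dates without a rule of their own, the condition "If both the day and the month are missing" leads to 1 July of the known year.

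The section opens permissively ("The following conventions may be used for imputing partial dates for analyses requiring dates"), but the death-date bullet itself is worded as a firm instruction.

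The death date enters OS directly, since OS is "defined as the time from randomization to the date of death from any cause" (SAP section 4.1.2). It enters DFS only for a death with no earlier recurrence, new anticancer therapy or new non-urothelial primary cancer (SAP Table 4.1.1-1). SAP section 7.6.1 also counts deaths within 30 and 100 days of the last dose, without saying whether imputed dates are used there.

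**The concern.** The missing-day rule picks the earliest date consistent with everything known. The missing-month rule does not: it drops the year. A subject last known alive in one calendar year and recorded as dying in a later one is given a death date that the record excludes. OS is then shorter than the data allow, and so is DFS where that death is the first event. If the table of deaths by time since last dose uses the imputed date, a late death could also be counted as an early post-treatment one. OS is formally tested in two populations, so its dates should not contradict the source record.

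**Working it through.** **1. When the rule contradicts the record.** Let L be the last known alive date and J be 1 January of the recorded year of death.

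- L on or after J: the imputed date L is possible, and is the earliest possible date. No conflict.
- L before J: the imputed date is impossible, and survival is understated by at least J − L.

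Examples: L = 10 November 2018 with death in 2019 gives at least 52 days. L = 15 March 2018 with death in 2020 gives 657 days, and 657 / 30.4375 = 21.6 months.

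**2. How often this happens among deaths with a missing month.** The documents give no frequency, so this rests on assumptions: death uniform over a year of Y = 365.25 days, and last contact uniform over a gap of g days before death (g ≤ Y). Then P(L before J) = g / (2Y), and the mean provable error in those cases is g / 3.

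| Assumed gap g | Share contradicting the record | Mean provable error |
|---|---|---|
| 3 months (91.3 days) | 12.5% | 30 days |
| 6 months (182.6 days) | 25% | 61 days |
| 12 months (365.25 days) | 50% | 122 days |

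The first row matches the planned contact interval (SAP section 4.1.2: "Survival follow-up will be conducted every 3 months").

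**3. Number of deaths.** An assumed 1–3% of 404 is 4 to 12 deaths.

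**4. Effect on the OS hazard ratio.** Inputs from SAP section 5: 700 subjects 1:1, 43 months of accrual, final OS analysis at about 105 months, median OS 4.6 and 6.5 years, exponential. Uniform accrual is assumed, so follow-up runs from 105 − 43 = 62 to 105 months.

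- Monthly hazards: ln 2 / 55.2 = 0.01256 and ln 2 / 78 = 0.00889. The ratio is 0.708 (plan: 0.71).
- Average probability of death by cut-off: 0.645 and 0.521. Times 350, this is 226 and 182 deaths, 408 in total (plan: 404).
- Person-months (deaths / hazard): about 17,985 and 20,518.

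Now move 3% of the deaths in one arm back by 21.6 months, which is far harsher than the table above.

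- Placebo only: 6.8 × 21.6 ≈ 146 person-months, or 0.81% of the arm's total. The hazard ratio falls by roughly 0.708 × 0.0081 ≈ 0.006. This overstates the change, because early deaths cannot be moved back the full amount.
- Nivolumab only: 5.5 × 21.6 ≈ 118 person-months, or 0.58%. The hazard ratio rises by roughly 0.004.

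Simulating trials under the same inputs, with the shift stopped at randomization, gives mean changes of −0.004 (placebo only), +0.004 (nivolumab only) and 0.0002 (both arms). The largest change in any single trial was about 0.013. With shifts of 0–3 months in 1% or 5% of deaths in both arms, the mean hazard ratio stayed at 0.712, power stayed at about 88%, and no single trial moved by more than about 0.002.

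The rule changes dates and not whether a death is counted, so the totals of 230, 303 and 404 OS events are not altered.

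**The case against.** The best defence is that the rule rarely matters. Contact is planned every 3 months, Protocol section 3.6 lets the sponsor request extra survival checks on all randomized subjects, and a gap as long as 21 months needs a subject truly lost to contact. The trial is double-blind and the rule is the same in both arms. All of this stands, and it is why the point is minor. It does not make an impossible date acceptable.

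It is also fair to say that 1 January is itself early and shortens survival for a death later in the year. That stands too: the proposed floor removes the contradiction with the record but does not make the date accurate.

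A reader might infer two stronger claims that the documents do not support.

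- **That registry searches produce these year-only deaths.** Protocol section 3.6.2 says "The site staff and representative will consult publicly available sources, such as public health registries and databases", but that sentence goes on to give updated contact details as the aim. The sentence before it does mention public vital status data, so a search may reveal a death. Nothing says that such sources give only a year, and the same section asks the site to obtain the date and cause of death.
- **That the error differs by arm.** Nothing in the documents points to unequal loss to follow-up. The one-arm figures in the working are a stress test, not an expectation.

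**Conclusion.** Wrong as written, minor. The missing-month rule discards a known year and can yield a death date that the record excludes. No other section corrects it. It would be too strong to say that all OS and DFS death times handled this way are too short by a provable amount: that holds only when the last known alive date precedes 1 January of the recorded year. For DFS, only deaths that count as first events are touched, and their number is not given, so no DFS effect is computed.

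On an assumed 1–3% of 404 OS deaths, the mean effect on the hazard ratio is about 0.004 or less even if one arm alone is affected. For scale, the target of 0.71 and the final boundary of 0.79 are 0.08 apart. The share of deaths, the contact gaps and the size of the shift are assumptions. The contradiction in the rule does not depend on them.

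**What to change.** Replace the missing-month-or-year sentence in SAP section 8 with:

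> If the month is missing and the year is known, the death date will be the later of 1 January of that year and the last known alive date. If the year is missing, the last known alive date will be used.

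This carries the SAP's missing-day logic up one level. In section 7.6.1, also state whether the 30-day and 100-day death tables use the imputed date. The cost is a sentence or two in the SAP and one line of derivation code, with no effect on data collection, sample size or alpha. It is best done before unblinding, since a later change to death dates could look data-driven.
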